### 3.3.3 Exclusion criteria

1. Part A only: For patient who has been treated with afatinib, last treatment at reduced dose below the assigned dose level
2. Patient whose disease progressed on insufficient dose of EGFR TKI immediately prior to study in the opinion of the investigator
3. Part B only: More than 2 prior EGFR TKI treatment regimens for relapsed or metastatic NSCLC
4. Chemotherapy, biological therapy or investigational agents (except EGFR TKIs) within 4 weeks prior to the start of study treatment.
5. Use of previous EGFR TKIs except afatinib within 3 days of treatment administered.
6. Radiotherapy within 4 weeks prior to the start of study treatment, except as follows:
  - (a) Palliative radiation to target organs other than chest may be allowed up to 2 weeks prior to the start of study treatment, and
  - (b) Single dose palliative treatment for symptomatic metastasis outside above allowance to be discussed with sponsor prior to enrolling.
7. Patients with active brain or subdural metastases are not eligible, unless they have completed local therapy and have discontinued the use of corticosteroids or have been on stable dose of corticosteroids for at least 4 weeks before starting study treatment. Any symptoms attributed to brain metastases must be stable for at least 4 weeks before starting study treatment.
8. Meningeal carcinomatosis.
9. Major surgery (as judged by the investigator) within 4 weeks before starting study treatment or scheduled for surgery during the projected course of the study.
10. Known hypersensitivity to afatinib, monoclonal antibody or the excipients of any of the trial drugs.
11. Prior severe infusion-related reaction to a monoclonal antibody
12. History or presence of clinically relevant cardiovascular abnormalities such as uncontrolled hypertension, congestive heart failure NYHA classification of 3 (Refer to [Appendix 10.3](#)), unstable angina or poorly controlled arrhythmia as determined by the investigator. Myocardial infarction within 6 months prior start treatment.
13. Female patients of childbearing potential (see [Section 4.2.2.3](#)) and male who are able to father a child who:
  - (a) are nursing or
  - (b) are pregnant or

Proprietary confidential information.

© 2016 Boehringer Ingelheim International GmbH or one or more of its affiliated companies. All rights reserved.  
This document may not - in full or in part - be passed on, reproduced, published or otherwise used without prior written permission.

(c) are not using an acceptable method of birth control (see [Section 4.2.2.3](#)) or do not plan to continue using this method throughout the study and/or do not agree to submit to pregnancy testing required by this protocol.

14. Any history of or concomitant condition that, in the opinion of the investigator, would compromise the patient's ability to comply with the study or interfere with the evaluation of the efficacy and safety of the test drug.
15. Previous or concomitant malignancies at other sites, except effectively treated non-melanoma skin cancers, carcinoma in situ of the cervix, ductal carcinoma in situ or effectively treated malignancy that has been in remission for more than 3 years and is considered to be cured.
16. Disease that is considered by the investigator to be rapidly progressing or life threatening such as extensive symptomatic visceral disease including hepatic involvement and pulmonary lymphangitic spread of tumour (subjects who are intended for urgent chemotherapy)
17. Requiring treatment with any of the prohibited concomitant medications listed in [Section 4.2.2](#) that cannot be stopped for the duration of trial participation.
18. Known pre-existing interstitial lung disease (ILD).
19. Any history or presence of poorly controlled gastrointestinal disorders that could affect the absorption of the study drug (e.g. Crohn's disease, ulcerative colitis, chronic diarrhoea, malabsorption).
20. Active hepatitis B infection active hepatitis C infection and/or known HIV carrier.
21. Use of alcohol or drugs incompatible with patient participation in the study in the investigator's opinion.
22. Previous treatment with agents targeting the IGF signalling pathway.
23. Patients unwilling or unable to comply with protocol in the opinion of the investigator
24. Previous treatment with EGFR TKI which can't be documented as either reversible or irreversible (Part B only)
25. Part B only: Prior treatment with third generation irreversible EGFR TKI (e.g. AZD9291 or CO-1686)

### 3.3.4 Removal of patients from therapy or assessments

#### 3.3.4.1 Removal of individual patients

A patient has to be removed from the trial in case any of the following criteria applies:

- A patient denies further trial participation (patients are free to discontinue their participation in this study at any time without the need to justify this decision).

Proprietary confidential information.

© 2016 Boehringer Ingelheim International GmbH or one or more of its affiliated companies. All rights reserved.

This document may not - in full or in part - be passed on, reproduced, published or otherwise used without prior written permission.

In this event, the patient will be asked to have their end of treatment assessments and the data collected until the point in time when withdrawal occurred will be included in the final analysis of the trial data. No further follow-up will be performed in case the patient does not agree to follow-up.

A patient has to be discontinued from study treatment in case any of the following applies:

1. A patient requests discontinuation of active treatment but agrees to be followed-up.
2. Documented progressive disease ([Section 5.1.2](#))
3. The patient is no longer able to participate in the study (e.g., AE, pregnancy, surgery, concomitant diagnoses, concomitant therapies or administrative reasons). The investigator may also stop a patient's treatment, if the patient is no longer able to attend study visits e.g. due to worsening of disease; in such a case the Investigator's reason for a patient's removal must be recorded on the appropriate page of the Electronic Case Report Form (eCRF).
4. Significant deviation from the protocol. The decision to continue or withdraw treatment will be made after discussion between the sponsor and the investigator.
5. Diagnosis of ILD.
6. Further dose reductions considered necessary but not allowed according to the protocol for both study drugs ([Section 4.1.4.3](#)).
7. An interruption of both drugs for more than 14 days as counted from the next planned treatment administration. If an interruption of more than 14 days is necessary and clinically justified, the patient may continue study treatment after discussion and agreement between the investigator and the BI Clinical Monitor.

Patient withdrawal will be documented and the reason for withdrawal recorded and discussed in the final study report.

As soon as a patient has withdrawn from the trial, the EOT visit should be performed where feasible. Every effort should be made to follow up patients in case an adverse event is still ongoing at the time of withdrawal.

All patients who are included into the trial (i.e. having given informed consent) will have their data entered into the trial database. This includes patients who are considered screen failures i.e. do not commence study drug treatment.

### 3.3.4.2 Discontinuation of the trial by the sponsor

Boehringer Ingelheim reserves the right to discontinue the trial overall or at a particular trial site at any time for the following reasons:

1. Failure to meet expected enrolment goals overall or at a particular trial site,
2. Emergence of any efficacy/safety information that could significantly affect continuation of the trial.

Proprietary confidential information.

© 2016 Boehringer Ingelheim International GmbH or one or more of its affiliated companies. All rights reserved.

This document may not - in full or in part - be passed on, reproduced, published or otherwise used without prior written permission.

3. Violation of GCP, the CTP, or the contract by a trial site or investigator, affecting the appropriate conduct of the trial.
4. Discontinuation of the clinical development programme with Xentuzumab (BI 836845) or the combination of Xentuzumab (BI 836845) with afatinib.
5. Any other administrative reason

The investigator / the trial site will be reimbursed for reasonable expenses incurred in case of trial termination (except in case of the third reason).

#### **3.3.4.3 Replacement of patients**

Replacement of entered patients is only applicable in part A before the determination of MTD.

Patients will be replaced for the assessment of Dose Limiting Toxicities in case of:

- 1) Patient's withdrawal during the first course of treatment for reasons other than DLT, e.g. patient no longer wishes to participate, or lost to follow up during first course
- 2) Patients who do not experience DLT, but miss more than one visit during the first course of treatment
- 3) Patients who do not experience DLT but miss  $\geq$  one Xentuzumab (BI 836845) administration or  $\geq$  5 doses of afatinib in first treatment course
- 4) Patients who miss one complete course at any time beyond the first course of treatment may be replaced after discussion between the sponsor and the investigator
- 5) Patients who are non-evaluable with respect to DLT

Patients that have been replaced might continue treatment in the trial upon agreement between investigator and sponsor however these patients will not be considered for the evaluation of MTD.

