### **4.3 TREATMENT COMPLIANCE**

Xentuzumab (BI 836845) will only be administered by trained staff in participating sites. Date and time of start and end of infusion, the exact amount of drug administered at each infusion will be documented in the eCRF/ study medication form.

Afatinib will be given in accordance with the protocol and the instructions of a site investigator.

The appropriate number of afatinib tablets for 4-week treatment course will be provided to patients to be self-administered at home. Patients will be asked to bring the remaining trial medication at the end of each 4-week course to the investigator site for a compliance check. The remaining film-coated tablets will be counted by the investigator/site staff and recorded at the investigator site. Discrepancies between the number of tablets remaining and the calculated number of tablets the patients should have taken must be documented and explained. At the end of each 4-week course, any remaining medication will be collected. If the patient is eligible for further treatment, a new bottle of study medication must be dispensed.

The investigator and/or the sponsor can withdraw a patient from the study in the event of serious and persistent non-compliance which jeopardizes the patient's safety or render study results for this patient unacceptable. For afatinib, a maximum of 6 consecutive doses or 7 non-consecutive doses may be missed for other reasons than drug-related AEs. Patients who miss afatinib treatment more frequently are considered non-compliant.

Afatinib should not be taken more than once a day. Patient experiencing emesis should not take a replacement dose.

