## 5.2.6 Dose Limiting Toxicity

The primary endpoint of Part A of this trial is the occurrence of Dose Limiting Toxicity (DLT).

For definition of DLT, it is essential that patients are treated sufficiently according to supportive care standards. DLT is assessed throughout the Part A. A study drug-related adverse event constitutes a DLT, if one of the following applies:

- CTCAE Grade 4 neutropenia ( $< 0.5 \times 10^9/L$ ) lasting  $\geq 7$  days
- Febrile neutropenia ANC  $< 1.0 \times 10^9/L$  with a single temperature of  $> 38.3^\circ C$  or a sustained temperature of  $\geq 38^\circ C$  for more than one hour.
- Documented infection with ANC  $< 1.0 \times 10^9/L$
- CTCAE Grade 4 thrombocytopenia ( $< 25.0 \times 10^9/L$ ) or CTCAE Grade 3 thrombocytopenia associated with bleeding requiring platelet transfusion.
- CTCAE Grade 2 or higher decrease in cardiac left ventricular function
- CTCAE Grade 2 diarrhoea lasting for 7 days or more, despite appropriate use of standard anti-diarrhoeal therapy
- CTCAE Grade  $\geq 3$  diarrhoea despite appropriate use of standard anti-diarrhoeal therapy for at least two days

Proprietary confidential information.

© 2016 Boehringer Ingelheim International GmbH or one or more of its affiliated companies. All rights reserved.

This document may not - in full or in part - be passed on, reproduced, published or otherwise used without prior written permission.

- CTCAE Grade  $\geq 3$  nausea and/or vomiting despite appropriate use of standard anti-emetics for at least three days
- CTCAE Grade  $\geq 3$  skin rash despite standard medical management as outlined in [Section 4.2.3.2](#)
- AST or ALT  $> 5x$  ULN (for baseline AST/ALT  $\leq$  ULN) or  $>$  (baseline value + 4x ULN) (for baseline AST/ALT  $>$  ULN)
- CTCAE Grade  $\geq 3$  fatigue/asthenia lasting for more than seven days
- CTCAE Grade  $\geq 3$  hyperglycemia lasting  $> 48$  hours
- All other non-hematologic adverse events of CTCAE Grade  $\geq 3$  (except alopecia, infusion reaction, and allergic reaction) leading to an interruption of afatinib and/or Xentuzumab (BI 836845) for more than 14 days until recovery to baseline or Grade 1, whichever is higher

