### 5.2.7 Maximum Tolerated Dose and recommended phase II dose

The Maximum Tolerated Dose (MTD) is defined as the highest dose level studied for which the incidence of DLT is no more than one out of 6 patients during the first course. DLTs occurring after the start of the second treatment course will be analyzed separately. DLTs will only be investigated in Part A of the study.

For the definition of DLT and determination of MTD refer to [Sections 5.2.6](#) and [4.1.3.1](#).

The MTD will be defined on the basis of DLT observed during the first treatment course only. However, also DLTs after that time period will be considered for the purpose of determination of recommended phase II dose (RP2D). The MTD, maximal administered dose, or a lower dose level will be chosen as the RP2D based on the totality of the safety data available. The discussion and agreement on dose selection between the investigator and the sponsor will be documented and communicated to all participating sites.

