6.3 PATIENTS SETS ANALYSED

The following analysis sets will be defined for this trial:

- Enrolled set (ENR)

This patient set includes all patients with informed consent given. The enrolled set will be used for patient disposition tables.

- Treated set (TS)

This patient set includes all patients who are documented to have received and taken at least one dose of any study medication during the treatment cycles (from day 1).

Proprietary confidential information © 2017 Boehringer Ingelheim International GmbH or one or more of its affiliated companies

The TS will be used for all planned safety and efficacy analyses.

- **MTD Set (MS)**

The MTD set defines the set of patients in the first part of the trial that are fully evaluable for determination of the MTD in the first treatment course. The MTD set will be used for some safety analyses in the first part, this is specified in the technical TSAP.

Patients in the TS who were replaced within the MTD evaluation period in the first part of the trial will be excluded from the determination of the MTD. Replacement of patients in the first part of the study is defined in Section 3.3.4.3 of the CTP. The final list of replaced patients is supplied by the Trial Clinical Monitor (TCM) no later than the last report planning meeting before the database lock for the safety analysis.

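### Part A patients stopped by drug toxicity short of a listed DLT can be replaced and dropped from the MTD count, which can therefore understate toxicity

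*Protocol*

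**What the plan says.** Protocol Section 3.3.4.3 allows replacement in Part A until the MTD is determined. Criterion 1 covers "Patient's withdrawal during the first course of treatment for reasons other than DLT", with unwillingness to continue and loss to follow-up as examples. Criterion 2 begins "Patients who do not experience DLT, but miss" and concerns more than one missed visit in course 1. Criterion 3 concerns DLT-free patients who miss one or more xentuzumab infusions or at least "5 doses of afatinib in first treatment course". None of the three excludes drug toxicity as the cause. Replaced patients may stay on treatment, but "these patients will not be considered for the evaluation of MTD".

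SAP Section 6.3 carries this into the MTD Set: "Patients in the TS who were replaced within the MTD evaluation period" are left out of the MTD determination. SAP Section 7.4.1 repeats the exclusion. Replacement is settled case by case and confirmed by the trial team before database lock. Neither section mentions drug-relatedness.

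The MTD is a Part A primary endpoint. Protocol Section 5.2.7 defines it as the "highest dose level studied for which the incidence of DLT is no more than one out of 6 patients during the first course". In the DLT list of Section 5.2.6, Grade 3 or higher non-haematological events that have no criterion of their own count only when "leading to an interruption of afatinib and/or Xentuzumab (BI 836845) for more than 14 days until recovery to baseline or Grade 1" or the higher of the two. A last, discretionary item lets investigators, with sponsor confirmation, call any other significant drug-related toxicity a DLT. Its example is an event that needs a dose reduction under the afatinib label.

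SAP Section 9.1 includes replaced patients when the RP2D is chosen.

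**The concern.** The replacement rule is meant to ensure that the MTD rests on patients with enough exposure to judge. But a patient may miss doses precisely because the combination was not tolerated. If that patient leaves the MTD Set and a newcomer who can take the doses comes in, the count no longer describes everyone who tried the dose. Protocol Section 4.3, on compliance, does separate causes: it limits the afatinib doses that "may be missed for other reasons than drug-related AEs". Section 3.3.4.3 makes no such separation.

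At stake is how firmly the MTD can be stated. Protocol Section 4.1.3.2 gives it as xentuzumab 1000 mg/week plus afatinib 40 mg/day, and that dose starts Part B. The decision turns on one or two events in six patients, so a single patient can change it.

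**Working it through.** **Step 1. Can drug toxicity trigger replacement without being a listed DLT?**

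| Drug-related event in course 1 | Action required | Listed in Section 5.2.6 as a DLT when |
|---|---|---|
| Grade 2 diarrhoea for 48 hours despite treatment | Pause afatinib (Table 4.1.4.3:1) | Grade 2 lasts 7 days or more |
| Grade 2 nausea or vomiting for 7 days | Pause afatinib (Table 4.1.4.3:1) | Grade 3 or higher despite anti-emetics |
| Grade ≥3 non-haematological event with no criterion of its own, e.g. mucositis | Pause afatinib and/or xentuzumab (Table 4.1.4.3:1) | Interruption exceeds 14 days |
| Grade 4 infusion reaction | Withdraw from treatment (Table 4.2.3.4:1) | Excepted from the residual criterion |

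Under Section 4.1.4.3 skipped infusions are not made up, so one skipped infusion meets criterion 3.

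Take the third row with no infusion missed and the discretionary item not used. With up to 4 afatinib doses missed, the patient counts as DLT-free. With a pause of 5 to 14 days, the patient is replaced. Above 14 days, it is a DLT. The middle band leaves the count.

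**Step 2. What the documents quantify.** They give no DLT rate, no replacement rate and no operating characteristics for the MTD rule. The one Part A figure is the maximum of 18 evaluable patients (Protocol Section 7.6). It reproduces as 3 dose levels × 6 = 18, but has no bearing on this point.

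**Step 3. Formulas.** All three inputs are assumptions:
- p: probability of a DLT as counted
- q: probability of a DLT-free patient being replaced because of drug toxicity
- r: probability that such a patient would have had a DLT on full dosing

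At dose level 2, the highest, the rule passes exactly when at most 1 of 6 has a DLT. If x is the DLT rate entering the rule, P(pass) = (1−x)^6 + 6x(1−x)^5. The rate is:
- x = p/(1−q) with replacement as written
- x = p if these patients are kept as DLT-free
- x = p+q if all count as not tolerating the dose
- x = p+qr if the target is the full-dosing DLT rate

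**Step 4. Numbers at p = 0.15.** For q = 0.10, replacement gives x = 0.15/0.90 = 0.167 and P = 0.335 + 0.402 = 0.737. Kept as DLT-free, x = 0.15 and P = 0.377 + 0.399 = 0.776. All counted, x = 0.25 and P = 0.178 + 0.356 = 0.534.

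| q | Replaced: x | Replaced: P(pass) | Kept as DLT-free: P(pass) | All counted: x | All counted: P(pass) |
|---|---|---|---|---|---|
| 0.10 | 0.167 | 0.737 | 0.776 | 0.25 | 0.534 |
| 0.20 | 0.188 | 0.686 | 0.776 | 0.35 | 0.319 |
| 0.30 | 0.214 | 0.620 | 0.776 | 0.45 | 0.164 |

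Over p = 0.10 to 0.30 and q = 0.05 to 0.30, the gap between replacing and counting all runs from 7 points (p = 0.30, q = 0.05: 0.387 − 0.319 = 0.068) to 56 points (p = 0.10, q = 0.30: 0.793 − 0.233 = 0.560).

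**Step 5. Direction against the full-dosing rate.** p/(1−q) lies below p+qr exactly when r > p/(1−q). At p = 0.15 the threshold is 16.7%, 18.8% or 21.4% for q = 0.10, 0.20 or 0.30. With q = 0.20:
- r = 0.50: full-dosing rate 0.15 + 0.20×0.50 = 0.25, P(pass) 0.534. Replacement, at 0.686, is too lenient.
- r = 0.10: full-dosing rate 0.15 + 0.20×0.10 = 0.17, P(pass) 0.729. Replacement, at 0.686, is too strict.

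**The case against.** The strongest objection concerns direction. A reader might infer that the rule simply biases the trial toward calling a dose tolerable. The documents do not support that. Criteria 2 and 3 remove only DLT-free patients, and criterion 1 only withdrawals not due to a DLT, so the patients at issue were never in the DLT numerator. Taking them out raises the observed DLT fraction from p to p/(1−q). Under the protocol's own DLT definition, replacement is stricter than keeping them as DLT-free. This stands, and the point has to be conditional.

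A reader might also infer that a residual-category event can be a DLT only when the pause exceeds 14 days. That overlooks the discretionary item in Section 5.2.6, whose example fits a Grade 3 mucositis leading to a reduced dose. This stands too, but the item permits such events to be counted and does not require it.

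The gap is also limited. Section 5.2.6 has separate criteria, without the 14-day condition, for Grade 3 or higher diarrhoea, nausea and vomiting, rash, fatigue and hyperglycaemia, and for transaminase rises and reduced left ventricular function. Many expected toxicities are therefore caught already.

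Section 4.3 does not contradict Section 3.3.4.3: one defines non-compliance, the other evaluability for DLT. It shows only that the distinction by cause was available.

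Finally, SAP Section 9.1 brings replaced patients into the RP2D choice, and most safety outputs use the Treated Set. That protects the RP2D, but leaves the MTD and its DLT count as they are.

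**Conclusion.** The point holds in conditional form. The replacement criteria do not separate drug toxicity from other causes, the DLT list leaves events that can feed them, and the SAP drops the affected patients from the MTD evaluation. The count understates toxicity if these events are regarded as dose-limiting, or if these patients' DLT risk on full dosing exceeds p/(1−q). Patients already stopped by toxicity plausibly exceed that threshold, but no figure in the documents shows it.

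For size, at an assumed p of 0.15 and q of 0.10, 0.20 or 0.30, the chance of passing is 74%, 69% or 62% with replacement, against 53%, 32% or 16% when all such patients count against the dose. The second series is the extreme case and uses a broader endpoint than DLT, so it is not an estimate of bias in the planned one. Nor do the documents say whether any Part A patient was in fact replaced because of toxicity. The change is worth making: the extra summary is cheap, does not depend on the direction of bias, and could alter how firmly the MTD is stated.

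**What to change.** In SAP Sections 6.3 and 7.4.1:

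- List every replaced Part A patient by dose level, with the criterion met, the reason and the drug-relatedness of any AE behind it.
- Add a sensitivity DLT summary per dose level that keeps patients replaced because of a drug-related AE in the denominator, counted (a) as no DLT and (b) as not tolerating the dose in course 1.
- State whether the MTD in Protocol Section 4.1.3.2 holds under both counts. Retained patients can take a level above six, so give counts and proportions and say how the one-in-six limit is then read.

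Protocol Sections 3.3.4.3, 4.1.4.3 and 5.2.6 should be reconciled on how omissions and withdrawals caused by toxicity are counted. Because the MTD is fixed and replacement applied only before that, rewording the criteria would not change this trial's count; the practical remedy is in the reporting.

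The cost is one listing and one table from data already collected, since SAP Section 6.3 already calls for a final list of replaced patients. The downside is a possibly less favourable DLT count at the chosen dose. If no patient was replaced for a drug-related AE, one sentence saying so closes the matter.
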